### **ProCog Study Design & Protocol**

#### Aims

To investigate the acute (24 hours) and chronic (4/8 weeks) effects of probiotics (Ecologic Barrier) on cognitive performance and mood in ageing adults.

#### **Design**

Double-blind, cross-over, randomised control trial. All outcomes measured at baseline, 23 hours, 4 weeks and 8 weeks (*see page 3 for explanation*).

#### Intervention

Ecologic Barrier© – daily intervention of 2g (5 billion CFU per day). Placebo (carrier) matched in appearance, smell and taste.

### **Cognitive Outcomes**

Based on the literature review to-date, exact tasks to be confirmed (see page 10 for justifications). Parallel versions required for multiple test points.

- An emotional recognition/decision task
- Rey Auditory Verbal Learning Test (RAVLT)
- Corsi blocks
- Switching task

#### **Mood Outcomes**

Based on the literature review to-date, exact tasks to be confirmed (see page 10 for justifications).

- Leiden Index of Depression Sensitivity revised (LEIDS-r)
- Positive and Negative Affect Schedule expanded (PANAS-x)
- State items from State Trait Anxiety Inventory

#### Additional outcomes/possible covariates (see page 6 for justifications)

[figure not shown]
- Dietary measures with a food frequency questionnaire (FFQ)
- Two-day food diary to be completed over the acute arm
- Perceived Stress Scale
- Centre for Epidemiological Studies Depression Scale (CESD)
- Faecal microbiota profile (baseline and 8 weeks. Samples will also be collected at 4 weeks with analysis subject to cognitive results)

**No. of Participants:** 30 based on previous studies and G\*Power calculation, see page 11.

#### **Exclusion criteria:**

Already a habitual user of probiotics, antibiotic treatment within last 3 months, no current diagnosis of and not currently receiving treatment for mental health disorder, gastrointestinal disorder, allergic to any ingredient of active or placebo treatment. Regular smoker. Participants must not consume probiotic or prebiotics supplements or live yoghurt throughout the course of study.

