### Schematic diagram of cross-over RCT

### Upon initial enquiry

- A list of inclusion/exclusion criteria will be provided for participant to self-assess eligibility.

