### Familiarisation day

- Double check that participants meet inclusion/ exclusion criteria
- Take demographic information (see below)
- Minimum 2 practice sessions of battery (one guided and one unsupervised)
- Provide first sample kit with instructions

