### Demographic information to be collected

Age

Gender

Ethnicity

Education level

Socio Economic Status

Height/weight/BMI

Regular medications

Smoking status – smoking can affect both the gut microbiome and cognitive function, therefore useful to know.

Alcohol consumption – as above, although perhaps only an effect of chronic drinking rather than acute or low/moderate alcohol consumption  $\rightarrow$  measured using AUDIT

Alcohol Use Disorders Identification Test (AUDIT) – short 10 item questionnaire developed by the WHO to assess alcohol consumption and highlight potential alcohol problems. https://www.drugabuse.gov/sites/default/files/files/AUDIT.pdf

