### Sample size power calculation

Previous parallel RCTs looking at the effect of Ecologic Barrier on cognitive or mood outcomes have used between 20 and 36 subjects per group. There are some acute prebiotic studies looking at mood/cognitive outcomes – a positive effect of an intervention was reported using 30 participants in a cross-over RCT and 23 in a parallel groups RCT.

Previously, effect sizes between 0.4 and 0.6 have been reported for probiotic intervention on tasks of attention and executive function.

G\*Power calculation based on a medium effect size of 0.5:

t tests-Means: Difference between two dependent means (matched
pairs)

```
Analysis:
             A priori: Compute required sample size
Input:
             Tail(s)
                                                    One
             Effect size dz
                                                    0.5
                                                    0.05
             α err prob
             Power (1-\beta \text{ err prob})
                                                    0.8
Output:
             Noncentrality parameter \delta
                                                    2.5980762
                                                =
             Critical t
                                                    1.7056179
                                                    26
             Df
             Total sample size
                                                    27
                 Actual power
     0.8118316
```

Based on this information, we should aim for a sample of N=30.

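### The mental health item under Exclusion criteria is worded as a condition of entry, so read literally it is reversed, and the gastrointestinal item beside it can be read either way

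*Protocol*

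**What the plan says.** The Exclusion criteria section of the protocol is one short paragraph. It opens with "Already a habitual user of probiotics, antibiotic treatment within last 3 months". It then gives "no current diagnosis of and not currently receiving treatment for mental health disorder, gastrointestinal disorder", followed by "allergic to any ingredient of active or placebo treatment" and regular smoking. A closing sentence restricts supplements and live yoghurt during the study.

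Three places rely on eligibility criteria:
- Upon initial enquiry: "A list of inclusion/exclusion criteria will be provided for participant to self-assess eligibility".
- Familiarisation day, in the visit schedule: "Double check that participants meet inclusion/ exclusion criteria".
- Familiarisation day, in the example timelines: the criteria are checked again at the start of the visit.

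The Aims describe the effects of interest as those "on cognitive performance and mood in ageing adults". Age otherwise appears only under "Demographic information to be collected", without a limit. The protocol text shows no list of inclusion criteria.

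**The concern.** An exclusion list works by one rule: if the statement is true of a person, that person is out. The probiotic, antibiotic, allergy and smoking items follow the rule. The mental health item does not, because it describes the person one would normally expect to let in. Applied as written, it gives the opposite of what such an item usually does. The gastrointestinal item follows it after a comma, so the reader cannot tell whether it shares the reversal.

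What is at stake is a clear and reproducible definition of who may enter. Mood is one of the two outcome domains, depressive symptoms are listed as an additional outcome or possible covariate, and faecal microbiota are profiled. Mental health and gastrointestinal status therefore bear on what the trial measures and on the people to whom its results apply. Anyone repeating the trial, or judging whether an entrant was eligible, needs these two items to have one meaning.

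**Working it through.** The point concerns wording, so the check is a reading of the text.

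**Step 1. Polarity of the neighbouring items.** Probiotic use, recent antibiotics, allergy and regular smoking are each stated positively: presence excludes.

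**Step 2. The mental health item.** The statement is true only when a person has no current diagnosis and is receiving no current treatment. There are four possible combinations:

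| Current diagnosis | Current treatment | Statement true? | Result as a literal exclusion | Result if diagnosis or treatment excludes |
|---|---|---|---|---|
| No | No | Yes | Excluded | Not excluded |
| Yes | No | No | Not excluded | Excluded |
| No | Yes | No | Not excluded | Excluded |
| Yes | Yes | No | Not excluded | Excluded |

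All four rows differ between the last two columns. The reversal is complete.

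**Step 3. The gastrointestinal item.** Two readings fit the sentence:
- The negation carries over the comma. The item is then also reversed, with absence of a disorder counting towards exclusion.
- The negation stops at the comma. The item is then a positive entry like its neighbours, and presence of a disorder excludes.

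The next entry, on allergy, is positive. The negation has therefore ended by then, but the text does not show whether it ended before or after the gastrointestinal item.

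**Step 4. Does another section settle the intent?** The Aims mention ageing adults and say nothing about mental or gastrointestinal health. The protocol never describes its own participants as healthy. The evidence in the justification table for the outcome measures comes from depressed patients, people with HIV-1 and healthy adults, so it does not identify the population either. The checks at the familiarisation day refer to the inclusion and exclusion criteria and are not tied to any other text.

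**Step 5. Inclusion criteria.** The initial enquiry step and both familiarisation day descriptions refer to inclusion criteria. None are shown, and no age limit appears. An adult of any age satisfies the criteria that are shown.

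**Step 6. Effect on the plan's figures.** The sample size section gives dz = 0.5, one-sided alpha 0.05 and power 0.80. With n = 27 the noncentrality is 0.5 × √27 = 2.598, the critical t on 26 degrees of freedom is 1.7056 and the power is 0.8118. These match the protocol, which then rounds up: "Based on this information, we should aim for a sample of N=30". None of these inputs depends on the eligibility wording, so correcting it changes none of these figures.

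**The case against.** The best defence is that nobody would follow the literal reading. It would turn away everyone free of mental health diagnosis and treatment, and the phrase is recognisably an inclusion condition under the wrong heading. The closing sentence on supplements and live yoghurt is also a requirement and not an exclusion, so the paragraph is loosely written throughout. Staff check eligibility again before baseline.

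Much of this stands. The intended meaning of the mental health item can be guessed, and staff would probably apply it. But a guess does not replace a stated rule, and no passage confirms it. The staff check uses the same criteria and so does not repair them. The closing sentence causes no confusion, because it is a separate sentence that names the participants as its subject; moving it would be a matter of layout. The ambiguity of the gastrointestinal item remains even for a reader who corrects the mental health item in their head.

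A reader might go further and infer three things that the documents do not support:
- **That this paragraph is the list handed to participants.** The protocol says that a list of inclusion and exclusion criteria will be provided, not that it is this text. The handout is not in the documents.
- **That the reversal makes the trial miss the population in the Aims.** The Aims define that population only as ageing adults, so a mental health item cannot miss it. Only the unstated age range bears on the Aims.
- **That the error adds variance in a sample of 30.** The design is a cross-over with sample size based on paired differences, so stable differences between people largely cancel. Harm to precision would need less stable scores, or a treatment effect that varies with diagnosis, and neither is shown.

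**Conclusion.** The point holds as a wording error in an operative eligibility rule. The mental health item is reversed for every combination of diagnosis and treatment, the gastrointestinal item has two opposite readings, and nothing else in the protocol resolves either. The size cannot be expressed as a number, and no figure in the plan changes. It does not follow that the wrong people will be enrolled, since staff probably know what was meant.

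The missing inclusion list and age range is secondary: it is mainly absent detail, not a misstatement. It applies to the text available, which lacks the title page and figures. The conclusion on polarity assumes only that items under an exclusion heading are meant to exclude.

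**What to change.** Reconcile the two items with their heading. Write them as separate entries in the same polarity as the rest of the list. If it is the sponsor's intent, this could read *current diagnosis of, or current treatment for, a mental health disorder* and, as its own entry, *gastrointestinal disorder*. The sponsor should also say whether the reference to current diagnosis or treatment is meant to apply to the gastrointestinal entry. Check that any list given to enquirers for self-assessment, and any form used at the familiarisation day, carries the corrected wording.

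Secondarily, add the inclusion criteria to which the protocol refers, with the sponsor's own age range for ageing adults.

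The cost is one reworded paragraph, a short inclusion list and a check of the handout. Design, visit schedule and sample size are untouched.

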### Schematic diagram of cross-over RCT

### Upon initial enquiry

- A list of inclusion/exclusion criteria will be provided for participant to self-assess eligibility.

### Familiarisation day

- Double check that participants meet inclusion/ exclusion criteria
- Take demographic information (see below)
- Minimum 2 practice sessions of battery (one guided and one unsupervised)
- Provide first sample kit with instructions

### T0 (baseline)

- Collect faecal sample
- Standardised breakfast
- Cognitive/mood battery
- Perceived Stress Scale
- Provide 2-day food diary to complete

[administer intervention immediately after baseline battery]

### T24

- Standardised breakfast
- Cognitive/mood battery
- Supply with 4 weeks' worth of treatment A and administration instructions
- Provide FFQ to complete

### W4

- Compliance check
- Collect faecal sample
- Standardised breakfast
- Cognitive/mood battery
- Perceived Stress Scale
- Supply further 4 weeks' worth of treatment A

#### W8

- Compliance check
- Collect faecal sample
- Standardised breakfast
- Cognitive/mood battery
- Perceived Stress Scale

## T0 (baseline arm 2)

- Collect faecal sample
- Standardised breakfast
- Cognitive/mood battery
- Perceived Stress Scale
- Provide 2-day food diary to complete

[administer intervention immediately after baseline battery]

# T23 (arm 2)

- Standardised breakfast
- Cognitive/mood battery
- Supply with 4 weeks' worth of treatment B and administration instructions

# W4 (arm 2)

- Compliance check
- Collect faecal sample
- Standardised breakfast
- Cognitive/mood battery
- Perceived Stress Scale
- Supply further 4 weeks' worth of treatment B

### W8 (arm 2)

- Compliance check
- Collect faecal sample
- Standardised breakfast
- Cognitive/mood battery
- Perceived Stress Scale

### Demographic information to be collected

Age

Gender

Ethnicity

Education level

Socio Economic Status

Height/weight/BMI

Regular medications

Smoking status – smoking can affect both the gut microbiome and cognitive function, therefore useful to know.

Alcohol consumption – as above, although perhaps only an effect of chronic drinking rather than acute or low/moderate alcohol consumption  $\rightarrow$  measured using AUDIT

Alcohol Use Disorders Identification Test (AUDIT) – short 10 item questionnaire developed by the WHO to assess alcohol consumption and highlight potential alcohol problems. https://www.drugabuse.gov/sites/default/files/files/AUDIT.pdf

### Additional measures

**Perceived stress** – previous studies suggest that probiotic intervention is effective at protecting cognitive function under acute stress. Unclear whether this would apply to general perceived stress as opposed to physically induced stress. Use Perceived Stress Scale (PSS) to measure perceived stress and potentially include as a covariate. Some studies also used the PSS as an outcome measure to see if a probiotic intervention itself has an influence on perceived stress. This outcome will be measured at baseline and all chronic timepoints.

Perceived Stress Scale – well validated measure of perceived stress drawing on thoughts and feelings from the past month. Has also been used previously as an outcome measure to examine whether a probiotic intervention can influence perceived stress, with mixed findings. https://www.northottawawellnessfoundation.org/wp-content/uploads/2018/04/PerceivedStressScale.pdf.

**A measure of habitual diet** – useful to know the habitual diet of the participants. Also, this may enable us to explore the idea that individual microbiome composition will influence response to probiotic intervention. Those with a naturally more diverse gut microbiota (and therefore possibly more diverse diet) may respond better to the treatment. Or vice versa?

There is therefore a trade-off between wanting to remove diet as a confound when looking at cognitive data and allowing participants to continue eating as normal in order to maintain normal gut composition. Therefore, our decision is to provide the standardised breakfast at

each test point to avoid acute effects of breakfast variation on cognitive performance. Food consumption throughout the rest of the study period won't be controlled but should be recorded in a **2-day food diary during the acute phase**, the rationale here being that it enables participants to maintain their normal diet.

Epic Norfolk FFQ – will be used to gain an idea of habitual diet over last year.

We may also want to include some questions after administration about tolerability of the intervention and any potential side effects.

**Example test day timelines** (based on testing no more than two participants at any one time to comply with COVID-19 rules)

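### Does naming the Perceived Stress Scale as both a possible covariate and a repeated outcome bias the 4- and 8-week treatment comparisons?

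*Protocol*

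**What the plan says.** The protocol's summary page lists the Perceived Stress Scale (PSS) under a heading that covers both roles, "Additional outcomes/possible covariates". The Additional measures section then says "Use Perceived Stress Scale (PSS) to measure perceived stress and potentially include as a covariate". It goes on to note that some studies used the scale as an outcome "to see if a probiotic intervention itself has an influence on perceived stress", and follows that directly with "This outcome will be measured at baseline and all chronic timepoints".

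The same section describes the scale as a "well validated measure of perceived stress drawing on thoughts and feelings from the past month" and reports earlier work on whether "a probiotic intervention can influence perceived stress, with mixed findings".

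The visit lists agree with this. PSS appears at T0, W4 and W8 of both arms and not at T24 or T23. At T0 the dosing note, "administer intervention immediately after baseline battery", comes after the list of assessments that includes PSS.

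No treatment-effect model is written down. The only test named is the paired t test in the sample size section, and it has no covariate.

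**The concern.** The stated aim is the effect of the probiotic on cognition and mood. A week 4 or week 8 PSS score is taken after randomised treatment has begun. Because the scale looks back a month, it describes roughly weeks 0 to 4 or weeks 4 to 8 on treatment. The protocol treats an effect of the probiotic on stress as an open question, so these scores may lie on the path from treatment to outcome. A model that adjusts for them estimates only the part of the effect that does not run through stress. That part is itself distorted if stress and the outcome share an unmeasured cause.

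Nothing in the text rules this adjustment out. If it were made and the probiotic does change stress, the 4- and 8-week results would answer a different question from the one in the aims, and the estimate could move in either direction.

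A second strand is that the PSS paragraph starts from whether protection under acute stress carries over to everyday stress: "Unclear whether this would apply to general perceived stress as opposed to physically induced stress". That is a question about whether the treatment effect varies with stress, which a main-effect covariate does not test.

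**Working it through.** **1. The protocol's own figure.** The inputs, from the sample size section, are dz = 0.5, one-sided alpha 0.05 and power 0.8. For n = 27 the noncentrality is 0.5 × √27 = 2.598 and the critical t on 26 df is 1.7056, giving power 0.8118. This matches the printed output. At N = 30 the power is 0.848. Neither figure involves PSS, so no stated number depends on this point.

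**2. What adjustment for on-treatment PSS would do.** The documents give no inputs for this, so the following are assumptions in SD units of the paired differences. The total effect is 0.50. The probiotic lowers PSS by *a*. The outcome falls by *b* per unit of PSS. With X the paired PSS difference (mean −*a*, SD 1) and Y the paired outcome difference:

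Y = (0.5 − *ab*) − *b*X + u, with var(u) = 1 − *b*²

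The mean of Y is (0.5 − *ab*) + *ab* = 0.5. The adjusted contrast is the intercept, 0.5 − *ab*. Power comes from 40,000 simulated trials of 30 pairs per setting, one-sided 0.05, 28 df for the adjusted test.

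| *a* | *b* | adjusted effect 0.5 − *ab* | adjusted power |
|---|---|---|---|
| 0 | 0.3 | 0.50 | 0.87 |
| 0 | 0.5 | 0.50 | 0.92 |
| 0.2 | 0.3 | 0.44 | 0.77 |
| 0.3 | 0.3 | 0.41 | 0.70 |
| 0.4 | 0.4 | 0.34 | 0.57 |
| 0.5 | 0.5 | 0.25 | 0.39 |
| −0.2 | 0.3 | 0.56 | 0.91 |

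Unadjusted power is 0.85 throughout. The table runs from a small gain, through a serious loss, to an inflated estimate. It shows what could happen under a model the protocol does not contain, and says nothing about how likely any row is.

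**3. Whether the text points to that model.** Three readings of the wording bear on this.

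- The covariate sentence is conditional, and the heading on the summary page is equally tentative.
- The sentence that schedules the repeat measurements begins by calling PSS an outcome, and it follows the remark on studies that used it as one. The natural reading is that weeks 4 and 8 serve the outcome role.
- A T0 score exists in each arm, listed ahead of the dosing note. Even if it were filled in shortly after the dose, a one-month recall makes the first-arm score a pre-treatment value in substance.

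One scale can supply a baseline covariate and a follow-up outcome without contradiction. Using it both ways is ordinary practice.

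**4. What a T0 covariate would do in this design.** Write a participant's score as person effect + period + treatment + γ × (first-arm T0 PSS) + error. The γ term is the same in both arms and cancels in the paired difference, so as a main effect the first-arm value leaves the within-person contrast unchanged. The second-arm T0 value does vary within a person, but it may still reflect the first treatment. The text shown gives no gap between arms, though a schematic may be missing. If there is such carry-over, using that value could also touch the second-arm acute comparison, so the absence of PSS at T24 and T23 does not by itself place the acute comparison beyond reach.

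**5. The interaction question.** For correlations of 0.2, 0.3 and 0.4 between first-arm T0 PSS and the paired treatment difference, the two-sided power at n = 30 is 0.19, 0.37 and 0.61. The aims list no such question.

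**The case for a change.** The strongest case for acting is that the cross-over design makes the choice of visit matter more than usual. Since the study-entry score cancels from the paired contrast, only period-specific scores can alter the result, and the week 4 and week 8 scores are among the few that would. An analyst hoping for precision is therefore drawn towards the unsafe ones. An unstated choice that can move the estimate either way is best closed before unblinding, and one sentence would do it.

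The principle stands: a treatment comparison meant to capture the total effect should not be adjusted for something the treatment may change. It also stands that the protocol does not name the visit.

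The step from there to a fault in this document does not stand. The objection is to what silence permits. The protocol commits to no adjustment and attaches the follow-up scores to the outcome role, and the covariate's time point is a routine entry in a statistical analysis plan, which may exist but is not at hand. Confining the covariate to T0 also buys little here, because the first-arm value changes nothing as a main effect and the second-arm value has its own weakness. The interaction test would be an added exploratory analysis of low power with no matching aim.

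**Conclusion.** No change to the protocol follows. It gives PSS two compatible roles and leaves the covariate's visit open, as protocols commonly do. The harm requires two things together: an analyst choosing an on-treatment score as covariate, and a probiotic effect on stress. The first is nowhere stated. The second is unsettled on the protocol's own account.

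Under the assumed values the adjusted effect ranges from 0.25 to 0.56 against a total of 0.50, and equals 0.50 whenever treatment leaves stress unchanged. Those values of *a* and *b* are assumptions throughout, so the true size is unknown. The sample size and the power at N = 30 are unaffected. This is a gap that an analyst fills sensibly by keeping week 4 and week 8 PSS as outcomes and taking any PSS covariate from before dosing.
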